## 8.5. Study size

A feasibility assessment from iKM identified 783 patients who met study eligibility criteria and initiated PB+FUL and CCI (Table 3).

The 1035 patients who initiated PB+FUL and CCI in the first- through third-line setting were selected for chart review (633 PB+FUL and CCI). During chart review, these patients' eligibility was confirmed and some patients were disqualified. The final sample size for analysis will consist of the confirmed eligible patients who initiated first-line PB+FUL CCI

**Table 3. Initial feasibility assessment**

[figure not shown]
Eligibility criteria	Patient count - Excluded	Patient count - remained
Documented diagnosis of hormone receptor-positive (estrogen receptor-positive or progesterone receptor-positive), human epidermal growth factor receptor 2-negative metastatic breast cancer (mBC) who received a qualifying treatment (i.e., palbociclib, letrozole, exemestane, anastrozole or fulvestrant) within the USON during the study identification period [1]	-	19,720
Aged 18 years at initial recorded diagnosis of mBC	1	19,719
Exclusion of patients enrolled in an interventional clinical trial during the study observation period	1216	18,503
Did not receive a treatment indicated for another primary cancer during the study observation period	1572	16,931
Received care at a USON site(s) utilizing the full EHR capacities of iKM at the time of treatment.	0	16,931
EHR data available from the USON site(s) where the patient received treatment are accessible for research purposes	0	16,931
Exclusion of patients with qualifying treatments (i.e., palbociclib, letrozole, exemestane, anastrozole or fulvestrant) received only prior to metastases date and not after metastatic diagnosis	2558	14,373
Exclusion of patients with start of first regimen more than 120 days after metastases date	1455	12,918
Exclusion of patients whose data are inaccessible for research purposes	5594	7,324
Initial cohort counts (patients who initiated the cohort-specific regimen in an appropriate LOT)		
PB+FUL: Palbociclib combination therapy with fulvestrant following as first-line or beyond therapy in the metastatic setting. Patients with evidence of prior treatment with CDK 4/6 inhibitors (ribociclib or abemaciclib) in the metastatic setting were excluded. Study identification period: 01 February 2015 - 31 December 2019.	-	840
CCI	1	1

PFIZER CONFIDENTIAL

Exclusion of patients who initiated qualifying regimens prior to the start of the study period (by cohort)		
PB+FUL	47	793
	First-line = 39	
	CCI [REDACTED]	
	Third-line = 2	
	Fourth-line = 1	
	Fifth-line or beyond = 3	
CCI [REDACTED]	[REDACTED]	[REDACTED]
Exclusion of patients with fewer than 2 visits after index (by cohort)		
PB+FUL	10	783
		First-line = 488
		CCI [REDACTED]
		Third-line = 53
		Fourth-line = 45
		Fifth-line or beyond = 105
[REDACTED]	[REDACTED]	[REDACTED]
Patients selected for chart review (PB+FUL and CCI [REDACTED] who initiated 1L-3L treatment; n= 1035)		
Exclusion of patients whose data were inaccessible for chart review	29	1006
Exclusion of patients who were not diagnosed with HR+ mBC	45	961
Exclusion of patients who were not diagnosed with HER2- disease	10	951
Exclusion of patients who did not receive a qualifying treatment	124	828
Exclusion of patients who participated in clinical trials	21	807
Exclusion of patients with other primary cancers	40	767
Exclusion of patients who do not receive 1L-3L qualifying treatment (sequencing activities performed during analysis)	52	715
Exclusion of patients with an index date prior to 01 Feb 2016 (by cohort)		
PB+FUL	-	428
CCI [REDACTED]	[REDACTED]	[REDACTED]
Final cohort counts		
1L PB+FUL	-	317
2L PB+FUL	-	78

| 1L CCI |

PFIZER CONFIDENTIAL

## 8.6. Data management

A description of the data sources to be used for this study is provided in **Section 8.4**. Operational definitions, periods of assessment and data sources of all data elements to be used for this study, along with descriptions of how raw data elements will be transformed into derived variables, is presented in **Table 2**.

The McKesson study team will collaborate with McKesson's Commercial Intelligence group to collect the structured iKM data that will be used for analysis. The Commercial Intelligence team will be provided with a Data Collections Variable List, which will detail the specific data elements that will need to be included in the study dataset. A Data Analyst will begin by generating high-level study sample counts that demonstrate attrition rates of the inclusion/exclusion criteria.

The study team will review the attrition count and the Data Analyst will proceed with collecting the remaining data elements on the Data Collections Variable List. The Data Analyst will perform an initial quality control check of the study dataset before providing the file to the study team's Biostatistician on a secure server. Once received by the Biostatistician, data validation will continue and will consist of, but is not limited to, quality control checks for appropriate values, logical sequences and quantity of missing values.

A list of patients eligible for chart review was generated by the Data Analyst and the Biostatistician applied the agreed upon sampling technique to identify the specific patients that underwent chart review. This list of patients was then securely transmitted to the Chart Review Team Manager. The chart review team consists of experienced oncology healthcare providers.

The McKesson study team led a training session with chart abstractors to discuss study specific considerations. Reference materials were provided to abstractors at this time. If chart abstractors have questions during the abstraction process, these were first raised to the Chart Review Team Manager. As needed, questions were escalated to the Outcomes Researcher and Principal Investigator.

[figure not shown]
Chart review was accomplished by use of a secure, web-based eCRF. The main purpose of the eCRF is to obtain data required by this non-interventional study protocol in a complete, accurate, legible and in a timely manner.

Analyses will be conducted using statistical analysis software (SAS®; SAS Institute Inc., Cary, NC, US) and/or R: A Language and Environment for Statistical Computing (R Foundation for Statistical Computing, Vienna, Austria) as appropriate.

### 8.6.1. Case report forms (CRFs)/Data collection tools (DCTs)/Electronic data record

As used in this protocol, the term CRF should be understood to refer to either a paper form or an electronic data record or both, depending on the data collection method used in this study.

PFIZER CONFIDENTIAL

A CRF is required and should be completed for each included patient. The completed original CRFs are the sole property of Pfizer and should not be made available in any form to third parties, except for authorized representatives of Pfizer or appropriate regulatory authorities, without written permission from Pfizer. McKesson shall ensure that the CRFs are securely stored at the study site in encrypted electronic and/or paper form and will be password protected or secured in a locked room to prevent access by unauthorized third parties.

McKesson has ultimate responsibility for the collection and reporting of all clinical, safety, and laboratory data entered on the CRFs and any other data collection forms (source documents) and ensuring that they are accurate, authentic/original, attributable, complete, consistent, legible, timely (contemporaneous), enduring, and available when required. The CRFs must be signed by the investigator or by an authorized staff member to attest that the data contained on the CRFs are true. Any corrections to entries made in the CRFs or source documents must be dated, initialed, and explained (if necessary) and should not obscure the original entry.

The source documents are the hospital or the physician's chart. In these cases, data collected on the CRFs must match those charts.

### **8.8. Record retention**

To enable evaluations and/or inspections/audits from regulatory authorities or Pfizer, McKesson agrees to keep all study-related records, including the identity of all participating patients (sufficient information to link records, e.g., CRFs and hospital records), copies of all CRFs, safety reporting forms, source documents, detailed records of treatment disposition, and adequate documentation of relevant correspondence (e.g., letters, meeting minutes, and telephone call reports). The records should be retained by McKesson according to local regulations or as specified in the research agreement, whichever is longer. McKesson must ensure that the records continue to be stored securely for so long as they are retained.

If McKesson becomes unable for any reason to continue to retain study records for the required period, Pfizer should be prospectively notified. The study records must be transferred to a designee acceptable to Pfizer, such as another investigator, another institution, or to an independent third party arranged by Pfizer.

Study records must be kept for a minimum of 15 years after completion or discontinuation of the study, unless McKesson and Pfizer have expressly agreed to a different period of retention via a separate written agreement. Record must be retained for longer than 15 years if required by applicable local regulations.

McKesson must obtain Pfizer's written permission before disposing of any records, even if retention requirements have been met.

## 8.7. Data analysis

Detailed methodology for summary and statistical analyses of data collected in this study will be documented in a statistical analysis plan (SAP), which will be dated, filed and maintained by Pfizer. The SAP may modify the plans outlined in the protocol; any major modifications of primary endpoint definitions or their analyses would be reflected in a protocol amendment.\*

### 8.7.1. Analysis sets

Separate analysis sets will be created to address the study objectives based on the cohorts of patients to be included (an overview of these analyses is presented in **Table 2**). For the primary and secondary objectives, the analyses will consist of patients who initiated first-line PB+FUL, CCI [REDACTED]

### 8.7.2. Derived and transformed data

Some of the data elements needed for the study objectives will be derived from available data during the analysis phase of the study. Details about these calculations are provided along with the operational definition in **Table 2**. Prior to constructing these variables, the McKesson biostatistician will perform data validation activities. Data validation will continue and will consist of, but is not limited to, quality control checks for appropriate values, logical sequences and quantity of missing values.

Missing data will be identified and reported in the results tables as percentages for all variables. If there is a large amount of missing or illogical data, a decision to include, exclude or impute that variable will be subsequently made based on the study sponsor's decision.

### 8.7.3. Statistical methods

#### Description of study enrollment

To be included in the study patients must meet each of the inclusion criteria and none of the exclusion criteria listed in **Sections 8.2.1-8.2.2**. Counts of patients excluded for each criterion will be summarized.

#### Description of patient demographic, clinical and treatment characteristics

Descriptive analyses will be conducted to evaluate the demographic, clinical and treatment characteristics overall, as well as for the cohorts and stratifications defined above. Results will be reported in aggregate. Categorical variables (e.g., ECOG performance status) will be reported as frequency and percentage. Continuous variables such as age will be reported as mean, standard deviation, median and range (minimum-maximum). In the case of missing observations, the number and percentage of missing values will be reported.

---

\* If the SAP is modified, the study protocol will be updated accordingly and re-submitted to the IRB.

All descriptive tables will be presented overall and for each of the Cohorts defined above and, as supported by the final sample size, stratified to present the results for the subgroups defined in **Section 8.2.4**.

### Clinical outcomes

Time-to-event outcomes, time to chemotherapy, rwDOT, TTNT, OS, rwTTP and rwPFS, will be assessed using the Kaplan-Meier method with 95% CIs, and summary tables of the number of events and censored patients at 6, 12, 18, 24, 30, and 36 months among those who initiated first-line PB+FUL. Further details about these calculations are presented in **Table 2**.

CCI

To reduce the effect of selection bias, the study team will first consider baseline variables/covariates compared among propensity score matched cohorts. The propensity score, defined as the probability of being initiated on PB+FUL treatment, will be estimated using a multivariate logistic regression model conditional on the baseline covariates (e.g., age, gender, ethnicity, body mass index (BMI), menopausal status, comorbidities, ECOG, stage of diagnosis, count of metastatic sites and site of metastases). Each individual will have a propensity score that represents the probability of being treated with PB+FUL. Pairs of treated and untreated subjects will be matched on the logit of the propensity score using a caliper of width equal to 0.2 of the standard deviation of the logit of the propensity score, as this caliper has been shown to be optimal in a range of settings.

Alternatively, if propensity score matching is not supported by the sample size, standardized or normalized inverse probability of treatment weighting (IPTW) using propensity score may be applied to balance baseline demographic and clinical characteristics between the 2 comparison cohorts. For standardized IPTW, the propensity score weight will be calculated as the inverse of the propensity score (1/propensity score), then create a weight reflect the sample size for each of the treatment groups, i.e.,  $(1/\text{propensity score}) * (\text{number of obs. in treatment A}) / (\text{number of obs. in entire study group})$ . For normalized IPTW, the weights will be calculated as the inverse of patients' estimated probability of being in treatment. Finally, the normalized weights will be calculated by dividing each weight by the overall mean weight. After weighting, the sum of weights attributed to each patient in a given cohort may not be equal to the sample size of this cohort, consequently, the effective sample size after weighting may be different than the original sample size (i.e., before weighting), although the total size of whole study population will not be changed.

Last, during analysis, multivariable Cox regression models will be used to further reduce bias associated with underlying characteristics of the patient populations that may affect treatment selection. Specifically, all variables will be fitted into a multivariable Cox proportional hazard regression model to assess independent associations between clinical outcomes and probability of an event (hazard ratio) adjusting for the influence of other variables within the model.

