5.4 COVARIATES

Table 1 presents the list of variables that will be considered for this study. Most data will originate from 1 of 2 sources: the iKM EHR database (structured data) or chart review (unstructured data), although some variables may be derived from these raw data sources (e.g., age from date of birth). Derived and transformed data needed for the analysis are described and presented along with the operational definitions in the table below.

For variables that are listed as being sourced from both structured and unstructured fields, chart review is recommended and, in some cases, may be required. Specifically, many of these are variables that are available in structured fields but have been found to be more reliably and comprehensively captured through chart review of unstructured fields. Other variables require information that can only be sourced through chart review (e.g., response and progression). Data elements listed as being “not reported” will be used to determine eligibility or in calculations of derived variables.

Variables described as being captured at “baseline” will be captured at the date closest to the index date initiation within 30 days (90 days for performance status). Variables described as being captured with “prior medical history” will be sourced from patients’ entire medical history within the USON prior to index treatment initiation. Other variable assessment periods are indicated below. If multiple values are available during the time period of measurement, the one closest (in absolute value) to treatment initiation will be used.

Some data elements will be captured from both iKM and chart review. Since the chart review data are expected to provide a richer source of information, if data are available from both sources for a single patient, then chart review data will supersede what is available in the structured iKM data for the final analysis.

Table 1. Study variables and operational definitions

Variable	Source(s)	Role(s) in study	Period of measurement	Operational definition
Demographic and patient characteristics				
Patient identification number	iKM structured data	Data linkage	Study observation period	Unique patient identifier that will be used to link clinical records. This information will not be disclosed to the study sponsor.

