Index treatment end date(s)	iKM structured data + chart review	Treatment characteristics	Study observation period	Date of final treatment for each drug or regimen. It is possible that the patient's treatment stop date is not documented if the patient dies, is lost-to follow-up or is still on-therapy. The final treatment date, death date or end of study date will be used, whichever is earliest.
Index line of therapy (LOT)	iKM structured data + chart review (derived)	Treatment characteristics	Study observation period	LOT will be assigned based on the absolute chronologic order of regimens, based treatment start and stop dates. Specifically, first-line treatment designation will be assigned to the first treatment received after metastatic diagnosis. Line of therapy will advance with each subsequent regimen.
Mean and median duration of index therapy	iKM structured data	Treatment characteristics	Study observation period	The duration (in weeks) between the start and stop of the index treatment regimen. Findings will be summarized as the mean (\pm SD) and median (range) of values.
Number of cycles (index treatment)	iKM structured data	Treatment characteristics	Study observation period	The number of provider-documented therapy cycles received for the index treatment. Findings will be summarized as the mean (\pm SD) and median (range) of values. The number of patients with available data will be reported.
Index treatment schedule (cycle length and frequency)	iKM structured data + chart review	Treatment characteristics	Study observation period	The planned frequency cycle length of the index treatment. Findings will be summarized as the mean (\pm SD) and median (range) of values. The number of patients with available data will be reported.
Index treatment schedule changes	Chart review	Treatment characteristics	Study observation period	Index treatment schedule changes will be captured and reported as the proportion of patients with changes.

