Reason for treatment discontinuation	Chart review	Treatment characteristics	Study observation period	
Data for discontinuation reason will exclusively come from chart review.
 
Reviewers will be asked to select reason(s) as explicitly documented in patients' charts.
 
If available, reason patients discontinued treatment will be abstracted:
 
Progression Toxicity Decline in performance status Financial/insurance Completed planned treatment Death Hospice Patient preference (if other categories do not apply) Physician preference (if other categories do not apply) Other

PFIZER CONFIDENTIAL

Proportion of patients who advance/do not advance	iKM structured data + chart review (derived)	Treatment characteristics	Study observation period	
The proportion of patients who advance and do not advance from the index treatment will be summarized as the count and percentage of the following:
 
Patients with ongoing index treatment
 
Patients who died following index treatment
 
Patients who advanced to a subsequent treatment
 
Patients who did not advance to a subsequent treatment for unknown reasons

Post-index treatment regimen	iKM structured data + chart review	Treatment characteristics	Study observation period	The regimen received by patients following discontinuation from the index treatment.
Time to chemotherapy	iKM structured data + chart review (derived)	Clinical outcomes	Study observation period	Time to chemotherapy will be defined as the interval (in weeks) between index treatment and start of chemotherapy as documented in the iKM EHR database. Patients with ongoing treatment at the study observation period will be censored on the study end date or the last visit date available in the dataset, whichever occurred first. rwDOT will be analyzed using the Kaplan-Meier method with 95% CIs, and summary tables of the number of events and censored patients at 6, 12, 18, 24, 30, and 36 months.

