				
(RECIST) criteria. However, the parameters underlying these criteria are less reliably available in retrospective, observational studies.²⁰ Instead, for this study, we will rely on provider documented assessments of response. No attempts will be made to mimic the RECIST guidelines.
 
Response assessments documented for the index treatment (depending on cohort). It is possible that patients have multiple response assessments in their charts during this period. All documented responses described in scan reports and progress notes (along with the associated note date) will be captured.
 
Response assessments will be classified as:
 
 Complete response: Documented as "a complete response" to therapy; indication patient is in "remission"; "all lesions" have disappeared or "no evidence of disease"). Response not otherwise specified (partial response or response not otherwise): any documentation of improved disease or responding disease not definitively classified as a complete response. Stable disease: Documented as disease is stable (not progressed or not improved; e.g. Stable appearance of lobe nodules). Mixed response: Combination of improved and worsened disease. Progressive disease: Documented as disease has "progressed"; or worsening of disease. Not evaluated: No documentation of status of disease.
Best overall response (BOR)	Chart review (derived)	Clinical outcomes	Study observation period	
Each patient will be assigned one BOR based on all recorded response assessments captured during chart review.
 
The responses will be ranked in the following order (from best to worst):
 
 Complete response Improved disease Stable disease Mixed response Progressive disease Not evaluated 
The proportion of patients with each BOR category will be reported.

Date of provider-documented progression or recurrent disease	Chart review	Clinical outcomes	Study observation period	
The date of provider-documented progression or recurrent disease as explicitly noted by a clinician in a scan report or progress note. Frequently, this will be the date the provider recorded evidence of progression, not necessarily the date the radiologic assessment was made.

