7 STATISTICAL METHODOLOGY AND STATISTICAL ANALYSES

7.1 STATISTICAL METHODS

Descriptive analyses will be conducted to evaluate the demographic, clinical and treatment characteristics for the study cohorts defined in Section 4. Results will be

PFIZER CONFIDENTIAL

reported in aggregate. Categorical variables (e.g., ECOG performance status) will be reported as frequency and percentage. Continuous variables such as age will be reported as mean, standard deviation, median and range (minimum-maximum). Chi-square testing will be used to assess associations between categorical variables when patient counts for single cells within the results tables are greater or equal to 5. When distribution cannot be assumed to be Chi-square, then Fisher's exact test will be used. Depending on normality, analysis of variance (ANOVA)/t-tests or Kruskall-Wallis tests will be used for continuous variables. An alpha level of 0.05 will be the primary criterion for statistical significance of this study.

Time-to-event outcomes will be assessed using the Kaplan-Meier method with 95% CIs, and summary tables of the number of events and censored patients at 6, 12, 18, 24, 30, and 36 months.

CCI

To reduce the effect of selection bias, the study team will first consider clinical outcomes compared among propensity score matched cohorts. The propensity score, defined as the probability of being initiated on PB+FUL treatment, will be estimated using a multivariate logistic regression model conditional on the baseline covariates (e.g., age, gender, ethnicity, body mass index (BMI), menopausal status, comorbidities, ECOG, stage of diagnosis, count of metastatic sites and site of metastases). Each individual will have a propensity score that represents the probability of being treated with PB+FUL. Pairs of treated and untreated subjects will be matched on the logit of the propensity score using a caliper of width equal to 0.2 of the standard deviation of the logit of the propensity score, as this caliper has been shown to be optimal in a range of settings. The propensity score will be used to select patients for chart review, as well as the single confounding variable during analysis. 1:n matching could be done by propensity score matching, n could be 1, 2, 3, etc.

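### For the two-cohort adjusted comparison, the SAP states two adjustment rules that cannot both be followed, and its fit-everything Cox rule overfits if taken literally

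*Protocol*

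**What the plan says.** Protocol 8.7.3 (Clinical outcomes) and SAP 7.1 give the same sequence for the cohort comparison: propensity-score matching, inverse probability weighting if the sample cannot support matching, and last a Cox regression.

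- The propensity score is to be "estimated using a multivariate logistic regression model conditional on the baseline covariates". Ten covariates are named as examples: age, gender, ethnicity, BMI, menopausal status, comorbidities, ECOG, stage, count of metastatic sites and site of metastases.
- SAP 7.1 adds a sentence that the Protocol lacks: the score will be used to choose patients for chart review, "as well as the single confounding variable during analysis".
- In both documents the Cox models are meant to "further reduce bias associated with underlying characteristics of the patient populations that may affect treatment selection". The rule that follows is that "all variables will be fitted into a multivariable Cox proportional hazard regression model".

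The visible text does not name the Cox covariates, their coding or a limit on their number. It does not say whether the model is fitted in the full, matched or weighted sample. The only list under the SAP's covariate heading (5.4) is introduced by "Table 1 presents the list of variables that will be considered for this study". That table holds baseline items, but also items known only after index: the cycle count ("The number of provider-documented therapy cycles received for the index treatment"), the reason for stopping ("Data for discontinuation reason will exclusively come from chart review") and best overall response ("Each patient will be assigned one BOR based on all recorded response assessments captured during chart review").

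**The concern.** An adjusted hazard ratio depends on what it is adjusted for. If the propensity score is the only confounder, the outcome model has two terms, cohort and score. If everything is fitted, it has from several dozen to more than a hundred. Someone must choose, and the timetable puts that choice late: Protocol Table 1 schedules descriptive analyses for September 2021, unadjusted outcomes for December 2021 and adjusted outcomes for January 2022. A covariate set left open until then can be settled with the unadjusted results in view.

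The larger model also has a technical cost. With few events per term, a Cox model tends to push the estimated log hazard ratio away from zero and to give confidence intervals that are too short.

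**Working it through.** **1. The two rules.** A single-confounder model and an all-inclusive model cannot both be the adjusted analysis. The single-confounder sentence also looks left over. It speaks of choosing charts by propensity score, but chart review ended in December 2020 (Protocol Table 1). All first- to third-line PB+FUL patients were taken: 783 − 45 fourth-line − 105 fifth-line or beyond = 633 (Protocol Table 3), the number selected in Protocol 8.5.

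**2. Number of terms.** The plan gives no event, power or covariate figure for this model, so there is none to reproduce. I counted from the categories in Protocol Table 2 (SAP Table 1), leaving out no-information levels.

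- Propensity list: age 1 + sex 1 + race 4 + BMI 1 + menopausal status 2 + comorbidities 31 + ECOG 3 + stage 8 (nine levels) + site count 3 + metastatic sites 12 = **66**.
- Other baseline items: ER and PR status 2 + height and weight 2 + smoking 2 + family history 1 + menopausal type 3 + region 3 + practice size 3 + physician volume 2 + specialty 2 + two times since diagnosis 2 + two endocrine-sensitivity flags 2 + visceral status 3 + histology 6 + BRCA, ESR1 and NGS 3 = 36. Running total 102.
- Prior treatment: adjuvant hormonal, (neo)adjuvant chemotherapy, metastatic hormonal, disease-free interval, surgery, radiotherapy = 6. Total **108**.

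**3. Patients.** After chart review 715 remain in both cohorts, and 428 are PB+FUL after the date cut. Comparators number at most 715 − 428 = 287 (the actual count is redacted). With 317 first-line PB+FUL patients, N is at most 317 + 287 = 604.

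**4. Events (assumed).** Survival is exponential, entry is uniform over 47 months, and follow-up runs from 6 to 53 months. Loss to follow-up is 0% or 15% per year. With λ = ln 2 / median, μ = −ln(1 − loss)/12 and h = λ + μ:

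event fraction = (λ/h) × [1 − (e^(−6h) − e^(−53h)) / (47h)]

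The survival inputs are figures cited in the Protocol background: median PFS 9.5 and 31.8 months, median OS 29.5 months, and 79.4% OS at 3 years. The last gives a median of 36 × ln 2 / −ln 0.794 = 108 months.

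Example, OS median 29.5 months without loss: h = 0.0235, and the fraction is 1 − (0.8685 − 0.2879)/1.104 = 0.474. Then 604 × 0.474 = 286 events. With the 108-month median and 15% loss the result is 82.

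**5. Events per term at N = 604**

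| Covariate terms | rwPFS (226–494 events) | OS (82–286 events) |
|---|---|---|
| 108 | 2.1–4.6 | 0.8–2.7 |
| 66 | 3.4–7.5 | 1.2–4.3 |
| about 17 (propensity list, collapsed; illustrative) | 13–29 | 4.8–17 |

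Matching would lower these figures. So would complete-case loss, because SAP section 6 rules out imputation. Endocrine sensitivity and disease-free interval are undefined for patients without adjuvant therapy, so an all-variable fit could drop that group.

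**6. Simulated Cox fits.** First setting: N = 604, 15% yearly loss, assumed medians of 20 and 50 months, 400 replicates. Covariates were drawn independently of cohort, so the result isolates overfitting. Mean HR is for a true HR of 0.70; type I error is for a true HR of 1, nominal 5%.

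| Covariates | Mean HR, 277 events | Type I error | Mean HR, 148 events | Type I error |
|---|---|---|---|---|
| 17 | 0.70 | 5.5% | 0.68 | 4.2% |
| 66 | 0.67 | 7.5% | 0.66 | 5.0% |
| 109 | 0.65 | 8.2% | 0.63 | 8.5% |

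Event counts are from the true-HR-0.70 runs (one to two events lower at 109 covariates). The Monte Carlo error on type I error is about 1.0 to 1.4 points. From 17 to 109 covariates the SD of the log HR rises from 0.12 to 0.17 and from 0.18 to 0.27.

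Second setting: 317 plus an assumed 200 comparators, about 180 events, true HR 0.70.

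- With 1,000 replicates, coverage of the 95% interval was 93.4% at 12 covariates, 92.2% at 60, 90.7% at 66 and 87% at 100. Mean HR was 0.70, 0.69 and 0.68 at 12, 60 and 66.
- Runs of about 150 replicates gave HR 0.67 and 88% at 60, 0.66 and 91% at 66, 0.64 and 88% at 100, and 0.65 and 85% at 108. The Monte Carlo error at 88% is √(0.88 × 0.12/150) = 2.7 points.

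**The case against.** A reader might infer that the plan orders adjustment for post-index variables, since the list under the SAP's covariate heading contains them. The documents do not support that. The sentence before the Cox rule limits the aim to characteristics that may affect treatment selection, which cycle count or stopping reason cannot do. The propensity model is limited to baseline covariates. The table's role column also marks cycle count and stopping reason as treatment characteristics and best response as a clinical outcome. That column does not settle the matter, because prior adjuvant therapy and disease-free interval also carry the treatment label. What remains is a risk from an open list.

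Further points for the sponsor:

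- *The steps may be sequential*, with Cox adjustment on top of matching. That is a sound design, but the score is then not the only confounder adjusted for, and the plan does not say which estimate leads.
- *Sixty-six terms are not forced.* Comorbidities are one item in the propensity list, with no coding given. Leukemia, lymphoma and other solid tumors should be nearly empty after the exclusion of other primary cancers. SAP 4.4 already has collapsed codings. This stands, and at 66 terms the loss is modest; but the text does not choose the smaller coding.
- *Redacted text and the embedded table shells could hold a list.* This also stands, so I do not claim that none exists. The visible Cox paragraph points to none, and the two visible SAP sentences conflict whatever is hidden.

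**Conclusion.** The contradiction within SAP 7.1 rests on the text alone. In the visible text the Cox covariate set is also undefined.

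Overfitting follows if the rule is taken literally. At 100 to 109 covariates a true HR of 0.70 is estimated at about 0.63 to 0.65, with coverage of about 85 to 88%, or type I error of about 8%. At about 66 the effect is smaller: HR about 0.66 to 0.68 and coverage about 91%. These sizes rest on assumed survival, loss and comparator numbers and are illustrative. Entry of post-index variables is a possibility that the wording leaves open, not something the plan prescribes.

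Only the two-cohort comparison is affected. The primary and secondary objectives use descriptive statistics and Kaplan-Meier estimates and do not depend on this model.

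**What to change.** - In Protocol 8.7.3 and SAP 7.1, replace the all-inclusive rule with a short named list of covariates and their coding. Size it to the expected events of each endpoint: even about 17 terms give only 4.8 events per term in the lowest OS scenario. Use the collapsed codings already in SAP 4.4 for stage, site count, ECOG and visceral disease, and a single comorbidity count.
- State that every covariate is measured on or before the index date and that no post-index variable enters the model.
- Delete the SAP sentence that makes the propensity score the only confounder, or replace it with a statement that the matched or weighted propensity-score estimate is the main one and the Cox adjustment is supporting. Say in which sample the Cox model is fitted, and align the Protocol.

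The cost is wording in two documents, with no new data. The downside is that some minor covariates are left out, with a little residual confounding from them. The change should be fixed before the adjusted analysis is run.
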